15.3.1 All Adverse Events

All adverse events will be summarized following statistics described in section 15.1.1.

Clinical trial.gov and EudraCT -requirements

In addition, a summary table will be provided for non-serious adverse events by SOC and PT per treatment group excluding SAEs applying

- frequency threshold of 5% based on crude incidence in either group

15.3.2 Serious Adverse Events

Serious adverse events will be presented following statistics described in section 15.1.1

Clinical trial.gov and EudraCT -requirements

In addition, a summary table will be provided for serious adverse events by SOC and PT per treatment group.

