## 5 Study design

This is a subject registry study with a non-experimental cohort design. The study will provide long-term follow-up of subjects who participated in Sponsor oral cladribine clinical trials in MS. Subjects will be enrolled through the clinical trial investigator or through the usual health care provider of the subject (cladribine clinical trial physician or otherwise) according to the health care system or to current medical practices in each of the participating countries.

Overall, the registry is prospective. However, lag interval information regarding exposure and events that occur between trial end and registry enrollment will be collected retrospectively.

Prospective collection of AEs in the ‘Blood and Lymphatic System Disorders’ and ‘Neoplasms Benign, Malignant, and Unspecified’ System Organ Classes (SOCs) and MS-related SAEs will be started upon local approval of protocol amendment 1 (version 2.0), dated 23 July 2012.

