#### 10.1.2 Opinion of External Experts and Scientific Boards

The cladribine DSMB provided guidance to the Sponsor during the development of the registry protocol. External experts from PPD also collaborated in the development of the Registry protocol.

The cladribine DSMB has been kept updated on the status of the registry since its initiation in 2009 and has been informed of all serious adverse events reported for subjects involved in the registry. As the cladribine development program has been terminated, the DSMB is no longer required. The DSMB will, however, continue to be informed of the progress of the registry until their final meeting late in 2012.

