9.2 Analysis Period

Analysis period for Safety Analysis Population and the DDI Safety Set

The analysis period for SAF and the DDI Safety Set is the time from the end of clinical trial + 1 day to the last date in PREMIERE.

Analysis period for Lymphocyte Analysis Population

Two analysis periods for lymphocyte analysis population are defined:

1. The time from first dose of cladribine/placebo* in clinical trials to the last absolute lymphocyte count (ALC) date with a value available in PREMIERE registry.
2. The time from first ALC date with a value in PREMIERE registry to the last ALC date with a value available in PREMIERE registry.

*** A subject who switches treatment from placebo to cladribine in subsequent studies/periods will be considered from first dose of cladribine and the placebo period will not be considered.**

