15.1 Primary Endpoints

15.1.1 Serious Adverse Events Related to Cladribine

Reporting will be done for SAF.

The objective is “to quantify and characterize the risk (cumulative incidence) of SADR, including malignancies and serious infections”.

Definition

The primary endpoint will be selected considering any serious adverse event characterized as Probable or Possible in the relationship to cladribine. Malignancies and serious infections will be considered in this endpoint only if the characteristics “serious” and “related” (“probable” or “possible”) are applicable.

Following protocol section 8.5.1.2, “an adverse drug reaction (ADR) is a response to a medicinal product which is noxious and unintended, and which occurs at doses normally used in man for prophylaxis, diagnosis, or therapy of disease or for the restoration, correction, or modification or physiological functions. Response in this context means that a causal relationship between a medicinal product and an adverse event is at least a reasonable possibility”.

The treating physician or other relevant concerned health care provider are asked to assess the relationship of the AEs to cladribine using the following definition, similar in all studies:

- Probable: A causal relationship is clinically/biologically highly plausible, and there is a correlation between the onset of the SAE and administration of cladribine, and between withdrawal of cladribine and resolution of the SAE.

- Possible: A causal relationship is clinically/biologically plausible and there is a correlation between the onset of the SAE and administration of cladribine.
- Unlikely: A causal relationship is improbable, and another documented cause of the SAE is most plausible.
- Unrelated: A causal relationship can be definitively excluded, and another documented cause of the SAE is most plausible.

The following statistics will be presented:

- Patient-year is the sum of the time since the end of clinical trial, expressed in years. Display with 1 decimal.
- m is the number of unique events. A unique event is a unique Preferred Term and date of onset per subject.
- n is the number of subjects with at least one event
- N is the total number of subjects in the treatment group
- AE (%) is the crude incidence. Display with 1 decimal.
 - $AE(\%) = (\text{number of subjects with at least one event} / \text{total number of subjects}) * 100$

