15.3 Adverse Events

Reporting will be done for SAF.

Adverse events are events that are reported with a start date on or after the end of clinical trial + 1 day [Registry Day 1].

AEs collected in PREMIERE either from AEs CRF Pages (AE dataset) or New Diagnoses CRF Pages (CE dataset) will be included.

Seriousness is not collected for events in the New Diagnoses CRF Pages. Seriousness will not be imputed and therefore these diagnoses will not be included in serious or non-serious AE tables.

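### Protocol dates prospective collection of MS-related SAEs from local approval of amendment 1, but the SAE tables use all time since trial end and do not mark the change

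*SAP*

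**What the plan says.** Protocol Section 5, repeated in the Synopsis, says that prospective collection of AEs in two SOCs and of "MS-related SAEs will be started upon local approval of protocol amendment 1 (version 2.0), dated 23 July 2012". Protocol 10.1.2 refers to the registry "since its initiation in 2009".

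Other protocol sections make no exception for MS-related events. Section 8.5.1.5 documents SAEs from the signing of consent to the last interview. Section 8.5.2 asks for complete data on all SAEs. For the lag between trial end and registry entry, 8.3.1.1 and 8.3.1.2 collect SAEs retrospectively by questionnaire or records review. Section 8.5.1.5 sends lag SAEs not reported in a prior trial to the sponsor's drug safety department.

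In the SAP, 15.3.2 states "Serious adverse events will be presented following statistics described in section 15.1.1" and adds a table by SOC and PT for ClinicalTrials.gov and EudraCT. SAP 15.3 counts events "reported with a start date on or after the end of clinical trial + 1 day". By SAP 9.2 the analysis period "is the time from the end of clinical trial + 1 day to the last date in PREMIERE". In SAP 15.1.1, "Patient-year is the sum of the time since the end of clinical trial, expressed in years", and crude incidence divides by every subject in the group. Neither these sections nor the list of changes in SAP Section 7 mentions the start of MS-related SAE collection.

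**The concern.** If Section 5 describes what was done, the numerator and denominator of the SAE tables cover different periods for one class of event. Time before local approval adds to patient-years, and a subject who left before approval still counts in N. In neither case was there prospective collection of MS-related SAEs. The expected direction is understatement of MS-related SAEs, and through them of all SAEs.

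The SAE table will be posted publicly by treatment group. The SAP also introduces a never-exposed group as a long-term reference, from which subjects who switched from placebo to cladribine are removed. If the two groups differ in source-trial mix, and so in when their post-trial time began, part of a difference between columns could reflect when collection started. The SAP repeats the disposition and special-interest tables by trial but not the SAE tables, so a reader could not check this.

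**Working it through.** The plan states no SAE rate or count, so there is no figure to reproduce. The check compares dates.

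**Inputs from the documents**
- Amendment 1 dated 23 July 2012 (Protocol 5). Local approval dates are not given.
- Source trials completed after November 2008 (Protocol 5.1). No end date is given for any single trial.
- Follow-up ends 8 years after first trial enrolment or at the end of the registry, whichever is first (Protocol 5.7). Last patient last visit was 25 October 2018 (SAP Section 6).

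**Assumptions**
- Time in trials, L: 2 or 4 years.
- Delay from the amendment date to local approval, d: 0 or 1 year.
- MS-related SAE rate: 0.5, 1 or 3 per 100 patient-years.

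**Share of post-trial time before prospective collection**

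With trial end T, amendment date A and end of follow-up E:

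share = (A + d − T) / (E − T), limited to 0–100%, where E is the earlier of T − L + 8 years and 25 October 2018.

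For L = 2, E − T = 8 − 2 = 6.00 years at every T below. With T = 1 December 2008 and d = 0, A − T = 3.64 years and the share is 3.64 / 6.00 = 61%.

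| Trial end | L = 2, d = 0 | L = 2, d = 1 | L = 4, d = 0 | L = 4, d = 1 |
|---|---|---|---|---|
| 1 Dec 2008 | 61% | 77% | 91% | 100% |
| 1 Jan 2010 | 43% | 59% | 64% | 89% |
| 1 Jan 2011 | 26% | 43% | 39% | 64% |
| 1 Jan 2012 | 9% | 26% | 14% | 39% |
| 24 Jul 2012 | 0% | 17% | 0% | 25% |

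These are shares of calendar time, not of events missed.

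**What that could do to incidence**

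Take the extreme case in which nothing MS-related is recorded before the amendment date, with L = 2, d = 0 and trial end 1 December 2008. Crude incidence is 1 − exp(−rate × time).
- At 1 MS-related SAE per 100 patient-years, full collection gives 1 − exp(−0.01 × 6.00) = 5.8%. The table would show 1 − exp(−0.01 × 2.36) = 2.3%.
- At 0.5 and 3 per 100 patient-years, the pairs are 3.0% against 1.2%, and 16.5% against 6.8%.
- For all SAEs, add an assumed 3 other SAEs per 100 patient-years. Full collection gives 1 − exp(−0.04 × 6.00) = 21.3%. The table would show 1 − exp(−0.03 × 6.00 − 0.01 × 2.36) = 18.4%.

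So even in this extreme case, total SAE incidence moves much less than the 61% share of time might suggest.

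**The case against.** The strongest answer is that MS-related SAEs may have been recorded throughout. Sections 8.5.1.5 and 8.5.2 cover all SAEs from consent, and Sections 8.2 and 8.4 ask about SAEs at every scheduled contact. The protocol text before the amendment is not available, so how complete recording was before 2012 is unknown. SAEs in the lag interval were sought retrospectively, and the time since trial end used above includes that lag.

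This stands in part. A reader might infer from Section 5 that MS-related SAEs went uncollected before approval, or that the calculated shares are minimum values. The documents support neither. Late approval raises a share, while lag collection recovers part of the events. That recovery has limits: it covers only trial end to registry entry, not enrolled time before approval, and Protocol 8.1 describes the records review as ascertaining SADRs, a narrower class than SAEs.

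The SAE table is also neither a primary nor a secondary endpoint. The primary SADR endpoint is confined to events judged possibly or probably related, and no formal inference is planned. This limits the consequence but does not remove it, because SAP 9.14 bases interpretation on point estimates and their intervals.

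**Conclusion.** The point holds in a limited form. Protocol Section 5 and the Synopsis conflict with 8.5.1.5 and 8.5.2 on when MS-related SAEs began to be collected, and they must be reconciled. If Section 5 governs, the tables in SAP 15.3.2 combine periods with different collection and are likely to understate MS-related and total SAE incidence.

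The size is unknown. The range of 0% to 61% rests on two years in trials, trial ends between December 2008 and July 2012, and approval on the amendment date. It is illustrative and bounds the bias in neither direction.

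Two further inferences go beyond the text. A reader might conclude that nervous-system SAE rows in particular are understated, but neither document says under which SOC MS-related events are coded. A reader might also attribute a difference between never-exposed and exposed columns to the collection date. The groups may differ through source-trial mix, but the documents show neither the size nor the direction of such an effect.

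**What to change.** First, state which protocol section describes actual practice before local approval of amendment 1.

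Then, in SAP 15.3.2, keep the all-SAE table and add:
- (a) SAEs excluding MS-related events, defined by a pre-specified PT list, over the full analysis period;
- (b) MS-related SAEs with onset from the site's amendment 1 approval date, with N and patient-years counted from that date;
- a separate listing of MS-related SAEs recorded before approval, including those from the lag interval, so that none are discarded.

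Footnote the change in collection in the SAE table and in the posted ClinicalTrials.gov/EudraCT table. A footnote alone would disclose the problem but leave the mismatch between events and time at risk.

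The cost is a PT list (neither document defines MS-related), the site approval dates and one extra table. The MS-related rows will rest on fewer subjects and patient-years, so their intervals will be wider.

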15.4 Deaths, Other Serious Adverse Events, and Other Significant Adverse Events

15.4.1 Deaths

Adverse events leading to death will be presented following statistics described in section 15.1.1.

15.5 Adverse Event of Special Interest

The term Adverse Events of Special Interest represents a broader than usual category of events for which specific attention will be paid during the review of the results.

The following statistics will be presented:

- Summary: Patient-year, number of unique event, number of subjects with at least one event, crude incidence and 95% CI per treatment group. All these statistics will be repeated for AE leading to death and serious AE.

In addition, summary table will be repeated by

- CLARITY only
 - CLARITY/CLARITY EXTENSION
 - ORACLE MS
 - ONWARD
- By PT: Number of patients with the AE and crude incidence (%) per treatment group and total will be presented.

15.5.1 AESI= Infections

Reporting will be regrouped into the 7 following AESI categories.

- AESI = Infections and Infestations

AESI = Infections and infestations is defined by any event belonging to the MedDRA SOC = Infections and Infestations.

- AESI = Severe Infections

AESI = Severe Infections is a custom grouping defined by any serious or severe event belonging to the MedDRA SOC = Infections and Infestations.

Data Handling

[REDACTED]

[REDACTED]

Adverse events collected under the New Diagnosis pages (PREMIERE eCRF only) does not have characteristics for severity being collected. However, AEs collected under the category “Other **severe** infections” will be considered for the definition of the AESI = Severe Infections.

- AESI = Herpetic infections

AESI = Herpetic infections is a custom grouping defined by any events from MedDRA HLT = Herpes viral infections.

- AESI = Opportunistic infections

The medical concept “opportunistic infections (including tuberculosis and PML)” is a custom grouping based on medical assessment. It includes MedDRA Preferred Terms (PTs) associated to viral, protozoal and bacterial infections as well as PTs associated to fungal infections with the exclusion of mucocutaneous and cutaneous fungal infections. Infections as provided by the US Centers of Disease Control (1993 revision) and in the Guidelines for the Prevention and Treatment of Opportunistic Infections in HIV-Infected Adults and Adolescents, <http://aidsinfo.nih.gov/guidelines> are included. PTs pertaining to the HLT ‘Herpes viral infections’ are not included.

This definition will be shortened in the tables footnote to read:

AESI = Opportunistic Infections is based on respective lists available in the context of HIV infections. It includes MedDRA preferred terms (PTs) associated to viral, fungal, protozoal and bacterial infections. PTs pertaining to the HLT ‘Herpes viral infections’ are not included.

The MedDRA terms that will be selected are listed in Appendix 18.3.

- AESI = Herpes zoster infections

AESI = Herpes zoster infections is a custom grouping defined by PTs with the term 'herpes zoster'.

The PTs that will be selected are listed in Appendix 18.4.

- AESI = PML

AESI = PML is a custom grouping defined by any events from MedDRA HLT = Polyomavirus infection.

- AESI = Tuberculosis

AESI = Tuberculosis is a custom grouping defined by any events from MedDRA HLT = Tuberculous infections.

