## 8.2 Schedule of Interviews and Subject Questionnaires

### Timing and Frequency of Interviews

On Day 1 of registry enrollment, the interviewer (PRP or trained site personnel) will verify that the informed consent has been signed and will proceed to administer the registry enrollment questionnaire.

During the first 2 years after enrollment into the registry the PRP or trained site personnel will interview the subject every 3 months. Thereafter, the contacts will be every year until the end of follow-up (see Section 13 [Appendix I](#), schedule of Interviews).

A window of  $\pm 2$  weeks around the date of the scheduled visit during the first two years and of  $\pm 4$  weeks thereafter, is acceptable. The structured questionnaire will be administered during routine clinical visits or by phone. The PRP or trained site personnel will enter the questionnaire responses collected in the electronic case report form. The completed questionnaires are source documents and will be filed with the registry participant's medical records on site, per Section 11.4 of the protocol.

At each scheduled contact, information on SAEs, AEs related to 'Blood and Lymphatic System Disorders' and 'Neoplasms Benign, Malignant, and Unspecified' SOCs, lymphocyte counts, and immunosuppressant medications will be collected through a structured questionnaire administered by phone or during a routine visit by the PRP or trained site personnel. A detailed schedule of interviews is provided in the Section 13 [Appendix I](#), schedule of Interviews.

**Pregnancies:** When a pregnancy is identified in a female subject, a specific pregnancy baseline questionnaire will be administered (see Section 8.3). During the pregnancy, the schedule of phone interviews will be adapted so that at least one such interviews takes place between months 4 through 7 after the last menstrual period (LMP), and another at month 10. After the end of the pregnancy, the schedule of interviews will shift to the regular periodicity.

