#### **8.3.1.2 Information from medical health records review**

For subjects with lagged data period, Sponsor will review data from medical records and the PRP will enter the following data into the registry participant electronic case report form:

- Treatment exposure to immunosuppressant medications, including type of treatment, and date started;
- Occurrence of SAEs including time and outcome;
- Occurrence of a pregnancy in participant woman, including date of LMP, and outcome;
- In subjects tagged as “lymphopenic subjects” ascertainment of performance of a blood test during the lagged data period, and categorization of lymphocyte counts as normal, Grade 1 through Grade 4 or unknown, if available.

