## 8.4 Follow-Up Interviews

For MS subjects, the information to be ascertained in the follow-up interviews fall into five main categories:

- Updates in contact information
- Occurrence of SAEs (including time of event and outcome)
- Occurrence of AEs in the ‘Blood and Lymphatic System Disorders’ and ‘Neoplasms Benign, Malignant, and Unspecified’ SOCs (including time of event and outcome)
- Capture of any lymphocyte count assessments performed since last visit
- Prescription of immunosuppressant medications including type and start date

It is expected that subjects in PREMIERE will attend their routine MS care visits. The PRP is expected to request blood count and differential if lymphopenia has not resolved (i.e., lymphocyte count is equal or greater than  $0.8 \times 10^9/L$ ). All lymphocyte count results will be captured by the PRP regardless of monitoring frequency. Participating PRP will be instructed to have blood count and differential performed at least yearly until resolution of lymphopenia (i.e., a Grade 1 or Grade 0 lymphopenia), or end of the study period.

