### 8.5.2 Recording of Adverse Events in the CRF (Methods of Recording and Assessing Adverse Events)

Complete, accurate, and consistent data on all SAEs experienced for the duration of the reporting period and on all AEs in the 'Blood and Lymphatic System Disorders' and 'Neoplasms Benign, Malignant, and Unspecified' SOCs will be reported on an ongoing basis in the appropriate section of the Case Report Form (CRF). In addition, all SAEs will be documented and reported using an SAE Form.

It is important that each report include a description of the event, its duration (onset and resolution dates/times), its relationship with cladribine, any other potential causal factors, any treatment given or other action taken, and its outcome.

The AE/SAE recording should comply with the following guidelines. Whenever possible, recognized medical terms should be used to describe AEs rather than colloquialisms (for example, "influenza" rather than "flu"), and abbreviations should be avoided.

- AEs/SAEs should be described using a specific clinical diagnosis, if this is available, rather than a list of component signs or symptoms (for example, "congestive heart failure" rather than "dyspnea, rales, and cyanosis").
- Signs and symptoms that are not linked (as "co-manifestations") to an identified disease or syndrome, or for which an overall diagnosis is not available, should be reported as individual events.
- Provisional diagnoses (e.g., "suspected myocardial infarction") are acceptable but should be followed up to a definite diagnosis if one becomes available.

Complete and appropriate data on all SAEs and on all AEs in the 'Blood and Lymphatic System Disorders' and 'Neoplasms Benign, Malignant, and Unspecified' SOCs experienced for the duration of the study will be reported on an ongoing basis in the corresponding pages of the CRF. It is important that each report includes a description of the event, its duration (onset and resolution dates or whether it is ongoing), its relationship to cladribine, any other potential causal factors, any concomitant treatment given or other action taken, and its outcome as of the end of the study.

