Secondary			

 To assess pregnancy outcomes, including congenital malformations or other important health conditions in the offspring born to women exposed to oral cladribine 	
 Pregnancy outcomes, including congenital malformations, spontaneous abortion, elective abortion, stillbirth, ectopic pregnancy, molar pregnancy, and other important health conditions in the offspring 	
 Number of patients with pregnancies from Registry Day 1 to End of registry and descriptive statistics of pregnancy outcomes 	
 Section 15.2

6 Overview of Planned Analyses

Summary of PREMIERE registry

The PREMIERE study is an ongoing prospective observational long-term safety registry of patients who have participated in at least one of the 5 cladribine clinical trials (namely CLARITY [25643], CLARITY EXT [27820], ONWARD [26593], ORACLE [28821] and the pantoprazole drug-drug interaction [DDI] phase I study [27967]). These 5 studies are referred throughout this document under the general term "clinical trials".

The original objectives of the PREMIERE registry were to monitor long-term safety events in a clinical trial population to produce long-term safety data in order to better characterize the potential safety risks of oral cladribine, and to build an evidence-based risk minimization strategy. The study was amended with simplification and including restriction to serious adverse drug reactions (SADR), selected AEs (all AEs in the 'Blood and Lymphatic System Disorders' and 'Neoplasms Benign, Malignant, and Unspecified' SOCs) and reduction of frequency of assessments. The duration of follow-up in the registry is up to the end of the registry or 8 years after the subject's first enrolment into a cladribine clinical trial, whichever occurs first. Last patient last visit for the final analysis was on October 25th, 2018.

[figure not shown]

Figure 1 PREMIERE Registry Overview Diagram

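### The SAP reports any-severity AE, infection, herpetic and zoster incidences over all subjects, although the protocol requires recording only of SAEs and AEs in two SOCs; these figures are minimum estimates and should be labelled so.

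*SAP*

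**What the plan says.** **Collection.** Protocol 8.2 sets the content of each contact: "At each scheduled contact, information on SAEs, AEs related to" the Blood/Lymphatic and Neoplasm SOCs, plus lymphocyte counts and immunosuppressants. In Protocol 8.4, "the information to be ascertained in the follow-up interviews fall into five main categories", and the only event categories among them are SAEs and AEs in those two SOCs. Protocol 8.5.2 requires "Complete, accurate, and consistent data on all SAEs experienced for the duration of the reporting period and on all AEs in the" two SOCs. For the lag interval, the enrollment questionnaire (8.3.1.1) covers the same events. The record review (8.3.1.2) lists "Occurrence of SAEs including time and outcome" but no other class of adverse event. Protocol section 5 starts prospective collection of the two SOCs only on local approval of amendment 1, dated 23 July 2012. SAP section 6 says: "The study was amended with simplification and including restriction to serious adverse drug reactions (SADR), selected AEs".

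**Reporting.** SAP 15.3.1 summarises all AEs with the 15.1.1 statistics. It adds a non-serious table by SOC and PT with a "frequency threshold of 5% based on crude incidence in either group". In SAP 15.5.1 the broadest infection category "is defined by any event belonging to the MedDRA SOC = Infections and Infestations", without regard to seriousness, and likewise herpetic infection (by HLT) and herpes zoster (by PT). SAP 15.3 draws events from both the AE pages and the New Diagnoses pages, and notes: "Seriousness is not collected for events in the New Diagnoses CRF Pages". Events from the latter are therefore left out of both the serious and the non-serious tables.

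**The concern.** An incidence is interpretable only if the event had a comparable chance of being recorded in everyone in the denominator. Infections and Infestations is not one of the two SOCs whose AEs must be recorded whatever their seriousness. A non-serious infection that nobody was required to enter, and nobody did, is counted as no infection.

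The exact interval makes the figure look precise, but it measures sampling error only. The topic matters: Protocol section 3 cites a risk ratio of 1.98 (95% CI 1.14 to 3.45) for herpetic infection in completed trials. A low registry figure for herpetic infection or zoster could therefore be read as reassurance when part of it reflects what was recorded. The non-serious table goes to public registries, where a reader will not see the collection rule unless it is stated.

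**Working it through.** **1. Required recording against planned reporting.**

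| Event class | Recording required (Protocol 8.2, 8.4, 8.5.2) | Reported as incidence (SAP) |
|---|---|---|
| SAEs, including serious infections | Yes | Yes: 15.3.2, and serious rows in 15.5 |
| AEs in the two SOCs | Yes, prospectively from local approval of amendment 1 | Yes: 15.1.2, 15.1.3 |
| Non-serious AEs elsewhere, including non-serious infections and zoster | No | Yes: 15.3.1, 15.5.1 |

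The third row is the mismatch. Protocol 9.2.2 planned cumulative incidence only for SADRs and the two SOCs, so the any-severity tables go beyond the events that the protocol set out to collect.

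**2. Denominator.** In SAP 15.1.1, N is every subject in the treatment group and patient-years are all time since the end of the trial. The window (SAP 9.2) opens the day after the trial ends, so it includes the lag interval. Neither is limited to periods when the CRF asked for the event, and no footnote on incomplete collection is planned. The crude incidence has no time term; follow-up enters only through the window and the patient-years shown beside it.

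**3. Direction.** Let I be the true any-severity incidence and e the share of events recorded. If events arise at a constant rate and each is recorded independently with probability e, the observed incidence is O = 1 − (1 − I)^e. For any e below 1, O is below I.

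**4. Illustration, not an estimate.** The documents give neither I nor e, so both are assumed. N = 1161 is the number of full participants (SAP section 7). The safety population is smaller by the drug-interaction study subjects, whose number is not given. Intervals are Clopper-Pearson, as in the SAP.

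| I | e | O | Subjects | 95% interval | Contains I? |
|---|---|---|---|---|---|
| 10% | 0.30 | 1 − 0.90^0.30 = 3.1% | 36 | 2.18% to 4.27% | No |
| 10% | 0.55 | 1 − 0.90^0.55 = 5.6% | 65 | 4.35% to 7.08% | No |
| 10% | 0.65 | 1 − 0.90^0.65 = 6.6% | 77 | 5.27% to 8.22% | No |
| 5% | 0.77 | 1 − 0.95^0.77 = 3.9% | 45 | 2.84% to 5.15% | Yes |

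With moderate under-recording the interval can miss the true value altogether. With a rarer event and better recording it need not.

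**5. The 5% threshold.** A term drops out of the non-serious table once e falls below ln(0.95)/ln(1 − I). For I = 10% that is 0.0513/0.1054 = 0.49; for I = 20% it is 0.0513/0.2231 = 0.23. Absence from the table therefore does not show that a term was infrequent.

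**6. What cannot be computed.** The documents give no event counts, no local approval dates, no CRF pages and no person-time by collection rule. No corrected incidence follows.

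**The case against.** Five points on the other side stand, wholly or in part.

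- **Non-serious infections were not shut out.** Protocol 8.5 has the standard interview ask about all clinically relevant health events, starting with non-leading questions. The New Diagnoses pages are a second source, with a category for other severe infections, which suggests that further infection categories existed. The CRF is not in the documents, so a specific zoster prompt can be neither confirmed nor excluded. A reader might infer that non-serious infections were never asked for. The documents do not support that; they show only that recording was not required.
- **The collection history is not documented.** One might try to size the problem from the calendar. From 23 July 2012 to 25 October 2018 is 6.26 years, and a 2009 start (Protocol 10.1.2) gives a registry span of 8.82 to 9.81 years, a share of 64% to 71%. That is not person-time in each subject's window, it assumes immediate local approval, and nothing describes what was collected before the amendment. It cannot be turned into a capture rate.
- **The reliable rows are already planned.** SAP 15.5 repeats each AESI summary for serious AEs, and 15.5.1 has a Severe Infections category.
- **Ratios may survive.** If recording was similar in exposed and never-exposed subjects, a ratio is roughly preserved. Differential recording between groups or parent trials is possible but not shown. No inference is planned, and these AESIs are not primary or secondary endpoints.
- **The New Diagnoses rule is disclosed.** The SAP says that seriousness will not be imputed, and the events stay in the all-AE and AESI tables.

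These points limit the claim about size. They do not remove the mismatch in the third row of the first table, or supply the missing label.

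**Conclusion.** The concern holds in a limited form. The SAP presents any-severity crude incidences for all AEs, non-serious AEs, any infection, herpetic infection and herpes zoster over all subjects, although the protocol requires recording only of SAEs and AEs in two SOCs. To the extent that other non-serious events went unrecorded, these figures are biased downward, and the exact intervals in the all-AE and AESI summaries do not show it. The direction follows from that one condition; the size is unknown.

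The serious-event rows, including SADRs, are not affected by this mechanism. Nor are the two-SOC rows, although their prospective collection began only on local approval of the amendment. In the Severe Infections category, events that were severe but not serious carry the same limitation unless a CRF page asked for them.

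A reader might conclude that the 5% table should be cut to the two SOCs. That would delete events that were recorded, and the shortened table would still span the change in collection at local approval.

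**What to change.** 1. **SAP 15.5.1:** make the serious-AE rows and the Severe Infections category the infection incidences that are interpreted with a confidence interval.
2. **Any-severity infection, herpetic, zoster and all-AE results outside the two SOCs:** present them as reported counts labelled *not systematically collected; minimum estimate*. Alternatively, restrict subjects and person-time to periods when the CRF asked for the events.
3. **The 5% non-serious table:** keep all recorded events. Footnote the restricted collection and its start at local approval of amendment 1, and repeat the note in the posted description.
4. **New Diagnoses events:** show them in a separate row for unknown seriousness, so that the serious and non-serious tables can be reconciled with the total.

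The labelling route costs SAP wording, footnotes and fewer rows with intervals, and needs no new data. The restricted-period route needs local approval dates and CRF versions. The downside is that there would be no headline incidence for infections of any severity.
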